### **Individual Concentration vs. Time Profiles**

- Individual concentrations will be plotted utilizing actual sampling times on the same figure.
- The terminal point selections will be indicated on a semi-logarithmic plot.

### **Average Concentration vs. Time Profiles**

- The average concentration profiles will be graphed using scheduled (nominal) sampling times.

- The average concentration profiles will be graphed using arithmetic average concentrations.
- The pre-dose average concentration for single-dose data from non-endogenous compounds will be set to zero. Otherwise, only quantifiable concentrations will be used to calculate average concentrations.
- Concentrations at a sampling time which are greater than  $\pm 10\%$  of the planned sampling time will be excluded from the average concentration profiles.
- Concentrations excluded from the mean calculation will be documented in the CSR.
- A concentration average will be plotted for a given sampling time only if 2/3 of the individual data at the time point have quantifiable measurements at actual sampling times which are within  $\pm 10\%$  of the planned sampling time. An average concentration estimated with less than 2/3 but more than 3 data points with quantifiable measurements that are within the sampling time as stated above may be displayed on the mean concentration plot if determined to be appropriate and will be documented within the CSR.

### **Treatment of Outliers during PK Analysis**

Application of this procedure to all PK analyses is not a requirement. Rather, this procedure provides justification for exclusion of data when scientifically appropriate. This procedure describes the methodology for identifying an individual value as an outlier for potential exclusion, but does not require that the value be excluded from analysis. The following methodology will not be used to exclude complete profiles from analysis.

#### Data within an Individual Profile

A value within an individual profile may be excluded from analysis if any of the following criteria are met:

- For PK profiles during single dosing of non-endogenous compounds, the concentration in a pre-dose sample is quantifiable.
- For any questionable datum that does not satisfy the above criteria, the profile will be evaluated and results reported with and without the suspected datum.

#### Data between Individual Profiles

1. If  $n < 6$ , then the dataset is too small to conduct a reliable range test. Data will be analyzed with and without the atypical value, and both sets of results will be reported.
2. If  $n \geq 6$ , then an objective outlier test will be used to compare the atypical value to other values included in that calculation:
  - a. Transform all values in the calculation to the logarithmic domain.

- b. Find the most extreme value from the arithmetic mean of the log transformed values and exclude that value from the dataset.
- c. Calculate the lower and upper bounds of the range defined by the arithmetic mean  $\pm 3*SD$  of the remaining log-transformed values.
- d. If the extreme value is within the range of arithmetic mean  $\pm 3*SD$ , then it is not an outlier and will be retained in the dataset.
- e. If the extreme value is outside the range of arithmetic mean  $\pm 3*SD$ , then it is an outlier and will be excluded from analysis.

If the remaining dataset contains another a typical datum suspected to be an outlier and  $n \geq 6$  following the exclusion, then repeat step 2 above. This evaluation may be repeated as many times as necessary, excluding only one suspected outlier in each iteration, until all data remaining in the dataset fall within the range of arithmetic mean  $\pm 3*SD$  of the log-transformed values.

#### Reporting of Excluded Values

Individual values excluded as outliers will be documented in the CSR. Approval of the CSR will connote approval of the exclusion.

### **9.3.2 Pharmacokinetic Statistical Methodology**

The PK parameters will be evaluated to estimate drug interaction for rosuvastatin with single (Day 6) and multiple (Day 13) doses of pirtobrutinib compared to rosuvastatin administered alone on Day 1. A participant may be excluded from the PK summary statistics and statistical analysis if the participant has an AE of vomiting that occurs at or before 2 times median  $t_{max}$ .

Log-transformed  $C_{max}$  and  $AUC(0-\infty)$  parameters for rosuvastatin will be evaluated in a linear mixed-effects model with a fixed effect for treatment, and a random effect for participant. Treatment can be rosuvastatin with single or multiple doses of pirtobrutinib, or rosuvastatin administered alone.

The least squares (LS) means for each treatment, the difference between the treatment LS means of

- 20 mg rosuvastatin + 200 mg pirtobrutinib on Day 6 (test) – 20 mg rosuvastatin on Day 1(reference)
- 20 mg rosuvastatin + 200 mg pirtobrutinib on Day 13 (test) – 20 mg rosuvastatin on Day 1 (reference)]

associated 90% CIs will be estimated from the model and back-transformed from the log scale to provide estimates of the geometric means, geometric mean ratio, and corresponding 90% CIs.

Example of the SAS code for the analysis:

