## 4. Study Design

### 4.1. Overall Design

Study J2N-MC-JZNW is a Phase 1, fixed sequence, open-label study in healthy participants that will investigate the effect of single and multiple doses of pirtobrutinib on the PK of rosuvastatin.

The schema in Section 1.2 illustrates the study design.

Approximately 36 participants will be enrolled to ensure that at least 28 evaluable participants complete the study.

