### 4.2. Scientific Rationale for Study Design

In order to allow each subject to act as their own control for safety and PK comparisons, a fixed sequence design has been selected.

This study will be open label as the study primary endpoint PK measures are objective rather than subjective.

Based on the  $t_{1/2}$  of rosuvastatin (19 hours; Crestor® Prescribing Information, 2020), a period of 4 to 5 days between rosuvastatin doses is considered sufficient time for the study intervention to washout. Based on the PK profile of pirtobrutinib, QD dosing for 7 days is considered sufficient time for pirtobrutinib to reach steady state.

The PK of rosuvastatin will be evaluated after a single pirtobrutinib dose on Day 6 to assess the effect on intestinal BCRP and after multiple pirtobrutinib doses on Day 13 to assess the effect on systemic BCRP.

Conducting the study in healthy participants mitigates the potential confounding effects of the disease state, other medical conditions, and concomitant medications in patients.

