**Other Exclusions**

13. Have c.34AA, c.421AA, or c.34GA/421CA genotypes of ABCG2 as determined through genotyping.
14. Have c.521TC and c/521CC genotypes of SLCO1B1 as determined by genotyping.
15. Are females who are lactating or have a positive pregnancy test.
16. Regularly use known drugs of abuse or show positive findings on drug screening.
17. Have donated blood of more than 500 mL within the previous 3 months of study screening.
18. Have an average weekly alcohol intake that exceeds 21 units per week (males) and 14 units per week (females). If calculation of units is required, use the following equation: Number of units = [total volume of drink (mL) × ABV (%)]/1000, where ABV is alcohol by volume.
19. Are unwilling to stop alcohol consumption 48 hours prior to admission and while resident at the CRU.
20. Use of tobacco- or nicotine-containing products within 1 month prior to check-in, or positive cotinine test at screening or check-in.
21. Are investigative site personnel directly affiliated with this study and/or their immediate families. Immediate family is defined as a spouse, biological or legal guardian, child, or sibling.
22. Are Lilly or Labcorp employees.
23. In the opinion of the investigator or sponsor, are unsuitable for inclusion in the study.

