**5.2.1. Rationale for Exclusion of Certain Study Participants**

The human BCRP transporter (also known as ABCG2) is polymorphic. Participants with the c.34AA, c.421AA, and c.34GA/421CA genotypes will be excluded because these genetic polymorphisms are associated with impaired BCRP activity (Furukawa et al. 2009, Wan et al. 2015, Keskitalo et al. 2009). Because the activity of BCRP is impaired with these participants, it would be anticipated that even complete inhibition of BCRP would not result in a substantial change in rosuvastatin exposure. Accordingly, excluding participants with these polymorphisms will ensure that the “worst-case” interaction between pirtobrutinib and rosuvastatin will be evaluated in this study.

The human OATP1B1 transporter (also known as SLCO1B1) is also polymorphic. In order to evaluate worst-case interactions between pirtobrutinib and rosuvastatin, participants with the c.521TC and c/521CC genotypes will be excluded from this study because this genetic polymorphism is associated with decreased transporting activity of OATP1B1 (Niemi et al. 2011) and higher plasma rosuvastatin concentrations (Crestor® Prescribing Information, 2020).

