### 9.1. Statistical Hypotheses

The primary objective variables will be evaluated to assess the potential DDI. No significant DDI for rosuvastatin will be concluded if the respective 90% confidence interval for area under the concentration versus time curve from time zero to infinity (AUC[0-∞]) and maximum observed drug concentration (Cmax) is completely contained within the no-effect boundaries (0.80, 1.25).

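### Does the single pooled residual in the primary mixed model give wrongly sized 90% confidence intervals for the Day 6 and Day 13 contrasts?

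*SAP*

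**What the plan says.** Protocol 9.3.1.2 and SAP 9.3.2 describe the same analysis: a "linear mixed-effects model with a fixed effect for treatment, and a random effect for participant". The SAP adds: "Treatment can be rosuvastatin with single or multiple doses of pirtobrutinib, or rosuvastatin administered alone". All three rosuvastatin profiles therefore enter one model, and the Day 6 minus Day 1 and Day 13 minus Day 1 differences, with their 90% intervals, are taken from it. The SAP then announces "Example of the SAS code for the analysis", and the code itself is blacked out. SAP 11 reports no departure from the protocol's analyses.

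Under Protocol 9.1, no significant interaction is concluded if the 90% intervals for AUC(0-∞) and Cmax lie wholly inside 0.80 to 1.25. On numbers, Protocol 4.1 says: "Approximately 36 participants will be enrolled to ensure that at least 28 evaluable participants complete the study".

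Two further places bear on whether the interaction might vary. Protocol 4.2 states the purpose of the Day 6 profile, taken with the first pirtobrutinib dose, and of the later one as follows: "to assess the effect on intestinal BCRP and after multiple pirtobrutinib doses on Day 13 to assess the effect on systemic BCRP". Protocol 5.2.1 says that in people with impaired BCRP activity "even complete inhibition of BCRP would not result in a substantial change in rosuvastatin exposure", and exclusion criterion 13 therefore bars those who "Have c.34AA, c.421AA, or c.34GA/421CA genotypes of ABCG2".

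**The concern.** A treatment effect plus a participant intercept, with nothing else named, implies one residual variance for all three days. With complete data the two primary contrasts then share one standard error. The Day 13 minus Day 6 difference, which is not a planned comparison, supplies a third of the weight behind it.

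If participants differ in how strongly pirtobrutinib affects them, the three pairwise differences can have unequal variances, and the pooled value may suit neither contrast. The protocol gives some reason to expect such differences. It ties the size of the interaction to BCRP activity, it does not exclude single ABCG2 heterozygotes, and it assigns different sites of action to Day 6 and Day 13.

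The intervals drive the only stated decision rule. An interval that is too narrow would raise the rate of false no-interaction conclusions, and one that is too wide would lose power.

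**Working it through.** **Inputs from the documents.** The model, the two contrasts and the 90% level (SAP 9.3.2); the limits 0.80 and 1.25 (Protocol 9.1); 28 evaluable completers (Protocol 4.1). The public text states no standard error, interval width, CV or power, so there is no plan figure to reproduce.

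**Assumed, because no document gives them.** Within-participant log SD s (0.25 unless stated); interaction SDs d6 and d13; correlation ρ between the two days' interactions.

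**Step 1: what the pooled model estimates.** With complete data the variances of the day differences are:

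- Day 6 − Day 1: 2s² + d6²
- Day 13 − Day 1: 2s² + d13²
- Day 13 − Day 6: 2s² + d6² + d13² − 2ρ·d6·d13

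The expected residual is one sixth of their sum. Doubling it gives the variance that the model assigns to both contrasts: 2s² + (2/3)(d6² + d13² − ρ·d6·d13). The point estimates are differences of day means under either analysis, so only the interval width is in question.

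**Step 2: when it is wrong, and in which direction.** Take d6 = d13 = d. The model uses 2s² + (2/3)(2 − ρ)d², and 2s² + d² is needed.

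- ρ = 0.5: (2/3)(1.5) = 1, so the pooled variance is exactly right.
- ρ = 1, d = 0.5s: SE ratio √(2.167/2.25) = 0.981.
- ρ = 1, d = s: √(2.667/3) = 0.943, too narrow.
- ρ = 0, d = s: √(3.333/3) = 1.054, too wide.

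Heterogeneity alone therefore does not imply mis-sizing, and its direction depends on a correlation that the documents do not give.

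**Step 3: effect on the decision.** Simulated trials, n = 28 complete, s = 0.25, true ratio 1.25, one parameter, nominal error 5%:

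| Interaction | Coverage | False no-interaction rate |
|---|---|---|
| None | 90% | 5.0–5.1% |
| Shared, d = 0.5s | 89.4% | 5.3% |
| Shared, d = s | 88.0% | 6.0% |
| d = s, ρ = 0.5 | 90% | about 5% |
| d = s, ρ = 0 | 91.6% | 4.2% |
| d6 = 0.5s, Day 13 adds an independent part of SD s | Day 13 87.5%, Day 6 93.4% | 6.3%, 3.4% |
| d6 = s, Day 13 adds an independent part of SD s | Day 13 86.7%, Day 6 91.6% | 6.6%, 4.2% |

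The last two rows need a large interaction spread: at a true ratio of 1.25, 21.2% and 26.4% of participants would have a reversed interaction on Day 13.

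The excess also depends on s. For shared d = s the error is about 6.0% at s = 0.25, 5.9% at 0.30, 5.0% at 0.35 and 2.9% at 0.40. If Cmax and AUC must both pass and both sit at the limit (correlation 0.8 assumed), it is 3.0% at s = 0.25.

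**Step 4: what the alternative costs.** Residual degrees of freedom fall from 2 × 27 = 54 to 27. The t multiplier rises from 1.674 to 1.703, a factor of 1.018. Power at a true ratio of 1, s = 0.25, moves from pooled to paired as follows:

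- no heterogeneity: 90.2% to 89.2%;
- shared d = 0.5s: about 87% to 85%;
- shared d = s: about 75% to 69%.

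Where the interaction is shared, part of the pooled model's power comes from its narrower interval, but the loss is still what a change would cost.

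**Step 5: incomplete data.** Equal standard errors are exact only for complete profiles. At an assumed CV of 30%, 28 participants on every day give 0.0785 for both contrasts. Counts of 36, 36 and 28 on Days 1, 6 and 13 give 0.0692 and 0.0758. The PK population in SAP 8 admits incomplete participants, so the standard errors may differ in practice, although the residual stays common.

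**The case for a change.** The strongest case for the concern is that the algebra is right, the mechanism has support in the protocol's own pharmacology, and the remedy is one sentence. Paired intervals held their error at 4.8–5.1% in the normal and two-point interaction scenarios. An unstructured covariance over the three days would do the same while keeping participants with a missing day. The plan already compares tmax separately for each contrast. In the less favourable patterns the pooled Day 13 error reaches 6.3% to 6.6%.

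The algebra stands, and so do those figures under their assumptions. The step from there to a defect does not. Protocol 5.2.1 explains why people with impaired BCRP activity are kept out, which reduces variation in response. It does not say that those who remain, including single heterozygotes, differ materially. Separate sites of action on Days 6 and 13 make unequal variances possible without indicating their size or how the days correlate. The prose names the fixed and random effects and does not exclude a richer residual structure in the redacted code. At an interaction SD of 0.5s or less, the gain in calibration is about as large as the cost in precision.

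**Conclusion.** The concern does not hold. The protocol and SAP specify the same valid model, nothing in either contradicts it, and the text that would show the covariance structure is redacted, which is not a gap in the plan.

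With 28 completers and s = 0.25, the departure from 5% is about 0.3 points at a shared interaction SD of 0.5s. It is about 1 point when that SD equals s and both days share the interaction fully, and it vanishes or reverses at between-day correlations of 0.5 or 0. It reaches 1.3 to 1.6 points for Day 13 only when the interaction is also more variable on that day. At s of about 0.35 or more, even the fully shared case with d = s is no longer above nominal. All of these sizes rest on assumed variances and correlations.

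Contrast-specific variances would be an equally respectable choice, with better calibration under some patterns and fewer degrees of freedom under all of them. Reasonable statisticians would differ on this, and the plan needs no correction.

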# CCI

The  $t_{max}$  will be analyzed non-parametrically using a Wilcoxon signed rank test. Estimates of the median difference comparing

- 20 mg rosuvastatin + 200 mg pirtobrutinib on Day 6 (test) – 20 mg rosuvastatin on Day 1 (reference)
- 20 mg rosuvastatin + 200 mg pirtobrutinib on Day 13 (test) – 20 mg rosuvastatin on Day 1 (reference),

corresponding 90% confidence intervals, and p-values from the Wilcoxon signed rank test will be calculated.

Example SAS code to be used for the Wilcoxon signed-rank test:

# CCI

## 9.4 Safety and Tolerability Assessments

### 9.4.1 Adverse events

Where changes in severity are recorded in the Case Report Form (CRF), each separate severity of the AE will be reported in the listings, only the most severe will be used in the summary tables. A pre-existing condition is defined as an AE that starts before the participant has provided written informed consent and is ongoing at consent. A non-TEAE is defined as an AE which starts after informed consent but prior to dosing. A TEAE is defined as an AE which occurs postdose or which is present prior to dosing and becomes more severe postdose.

All AEs will be listed. TEAEs will be summarized by treatment, severity and relationship to the study drug. The frequency (the number of AEs, the number of participants experiencing an AE and the percentage of participants experiencing an AE) of TEAEs will be summarized by treatment, Medical Dictionary for Regulatory Activities (MedDRA) version 24.1 system organ class and preferred term. The summary and frequency AE tables will be presented for all causalities and those considered related to the study drug by the investigator. Any serious AEs will be listed.

Discontinuations due to AEs will be listed.

#### **9.4.2 Concomitant medication**

Concomitant medication will be coded using the WHO drug dictionary (Version September 2021). Concomitant medication will be listed.

#### **9.4.3 Clinical laboratory parameters**

All clinical chemistry and hematology data will be summarized by parameter, along with changes from baseline, where baseline is the Day 1 predose assessment, and listed. Urinalysis data will be listed. Additionally, clinical chemistry, hematology and urinalysis data outside the reference ranges will be listed and flagged on individual participant data listings.

#### **9.4.4 Vital signs**

Vital signs data will be summarized by timepoint together with changes from baseline, where baseline is defined as the Day 1 predose assessment. Figures of mean vital signs and mean changes from baseline profiles will be presented by timepoint.

Values for individual participants will be listed.

#### **9.4.5 Electrocardiogram (ECG)**

ECGs will be performed for safety monitoring purposes only and will not be presented. Any clinically significant findings from ECGs will be reported as an AE.

#### **9.4.6 Hepatic Monitoring**

##### **Close hepatic monitoring**

If a participant who had normal or near normal baseline alanine aminotransferase (ALT), aspartate aminotransferase (AST), alkaline phosphatase (ALP), total bilirubin (TBL) (i.e.,  $<1.5 \times$  upper limit of normal [ULN]), experiences elevated  $ALT \geq 3 \times$  ULN,  $AST \geq 3 \times$  ULN,  $ALP \geq 2 \times$  ULN, or  $TBL \geq 2 \times$  ULN, laboratory tests should be repeated within 48 to 72 hours, including ALT, AST, ALP, TBL, direct bilirubin, gamma-glutamyltransferase, and creatinine kinase to confirm the abnormality and to determine if it is increasing or decreasing.

In participants enrolled with elevated baseline ALT, AST, ALP or TBL ( $\geq 1.5 \times$  ULN), the thresholds for close monitoring are  $ALT \geq 2 \times$  baseline,  $AST \geq 2 \times$  baseline,  $ALP \geq 2 \times$  baseline, or  $TBL \geq 1.5 \times$  baseline (except for participants with Gilbert's syndrome).

At a minimum, this evaluation should include physical examination and a thorough medical history, including symptoms, recent illnesses, (for example, heart failure, systemic infection, hypotension, or seizures), recent travel, history of concomitant medications (including over-the-counter), herbal and dietary supplements, history of alcohol drinking, other substance abuse and additional laboratory tests and/or abdominal imaging studies, as medically indicated.

If the abnormality persists or worsens, clinical and laboratory monitoring, and evaluation for possible causes of abnormal liver tests should be initiated by the investigator in consultation with the Lilly-designated medical monitor.

### **Comprehensive hepatic evaluation**

If a study participant, who had baseline ALT, AST, ALP, TBL $<1.5\times$  ULN, experiences elevated ALT $\geq5\times$  ULN, AST $\geq5\times$  ULN, ALP $\geq3\times$  ULN, TBL $\geq2\times$  ULN (except for participants with Gilbert's syndrome), or elevated ALT, AST $\geq3\times$  ULN with hepatic signs/symptoms (severe fatigue, nausea, vomiting, right upper quadrant abdominal pain, fever, rash, and/or eosinophilia $>5\%$ ), a comprehensive evaluation should be performed to search for possible causes of liver injury.

In participants who had elevated baseline ALT, AST, ALP, or TBL ( $\geq1.5\times$  ULN), the thresholds for performing this evaluation are ALT $\geq3\times$  baseline, AST $\geq3\times$  baseline, ALP $\geq2\times$  baseline, TBL $\geq2\times$  baseline (except for participants with Gilbert's syndrome), or ALT, AST $\geq2\times$  baseline with hepatic signs/symptoms.

At a minimum, this evaluation should include physical examination and a thorough medical history, as outlined above, as well as tests for prothrombin time-international normalized ratio, viral hepatitis A, B, C, E, tests for autoimmune hepatitis, and an abdominal imaging study (for example, ultrasound or computed tomography scan).

### **Additional hepatic data collection in participants who have abnormal liver tests during the study**

Additional hepatic safety data collection should be performed in participants who meet 1 or more of the following 5 conditions:

1. Elevation of serum ALT to  $\geq5\times$  ULN on 2 or more consecutive blood tests (if baseline ALT $<1.5\times$  ULN)
  - In participants with baseline ALT $\geq1.5\times$  ULN, the threshold is ALT $\geq3\times$  baseline on 2 or more consecutive tests
2. Elevation of serum TBL to  $\geq2\times$  ULN (if baseline TBL  $<1.5\times$  ULN) (except for cases of known Gilbert's syndrome)
  - In participants with baseline TBL  $\geq1.5\times$  ULN, the threshold should be TBL  $\geq2\times$  baseline
3. Elevation of serum ALP to  $\geq2\times$  ULN on 2 or more consecutive blood tests (if baseline ALP  $<1.5\times$  ULN)
  - In participants with baseline ALP $\geq1.5\times$  ULN, the threshold is ALP  $\geq2\times$  baseline on 2 or more consecutive blood tests
4. Hepatic event considered to be an SAE
5. Discontinuation of the investigational product due to a hepatic event

Where applicable, the following will be presented. The participants' liver disease history and associated person liver disease history data will be listed. Any concomitant medications that have potential for hepatotoxicity, including acetaminophen will be listed. Results from any hepatic monitoring procedures, such as a magnetic resonance elastography scan, and biopsy assessments will be listed, if performed.

Hepatic risk factor assessment data will be listed. Liver related signs and symptoms data will be summarized by treatment and listed. Alcohol and recreational drug use data will also be listed.

All hepatic chemistry, hematology, coagulation, and serology data will be listed. Values outside the reference ranges will be flagged on the individual participant data listings.

